5.3.2. Physiotherapy & Exercise

Subjects will be instructed to go about their daily lives as best as possible, and encouraged to be active.

If the Subject has previously participated in an exercise program or other physical activity (e.g.: aerobic exercises, weight training, home exercise machine, team or solo sports) then that exercise may continue or resume at the discretion of the Investigator, following the Randomization Visit. Such exercise should not be performed between Implant and the Randomization Visit to allow time for healing of the surgical scar.

Any additional exercise is to be allowed at the discretion of the Investigator, subject to the Subject's ability to perform exercise. To avoid bias, no specific physiotherapy or other exercises to treat CLBP are allowed between the Baseline and Primary Outcome Assessment Visit.

Strenuous activity that could exacerbate the underlying condition of low back pain shall be forbidden until after the Primary Endpoint Assessment Visit (e.g.: chopping wood, rowing, heavy weight lifting, and wrestling).

5.3.3. Other Devices or Therapy

Use of other devices or therapy is likely to confound the results of the Trial. Therefore, with the exception of medication, all therapies targeted at the low back pain will be prohibited during the Trial. Subjects should be instructed to not use any other devices such as braces, belts, TENs devices, acupuncture, chiropractic manipulation, massage or anything else which is not specifically required by this protocol.

It is especially important that the following procedures *not* be performed during the Trial because they will directly affect the device itself and/or its ability to interact appropriately with the body, or may affect endpoint assessment:

- Epidural injections
- Nerve ablations of any kind for low back pain
- Any other interventional pain procedures for low back pain (e.g.: nerve blocks)
- Any physical procedure (e.g.: back or gluteal massage or chiropractic adjustment) that carries a risk of dislodging leads

6. Subject Contact and Data Collection Schedule

Subject contact will be according to the following schedule. Any unscheduled visits will be recorded.

Note: All data collection shall be done as the first thing in the follow up visit, prior to any other procedures.

Note: Adverse event data will be collected at each visit after the Baseline Visit.

6.1. Visit 1: Informed Consent, Baseline Data, Inclusion Decision

The process for obtaining informed consent shall be in compliance with FDA regulations (21CFR 50) and ISO 14155.

Subjects will be provided with the Subject Information and Informed Consent Form which advises that data will be collected for evaluation of eligibility for inclusion in the Trial. Subjects are told that if the criteria are met and the Subject consents, then the ReActiv8 will be implanted.

If the Subject agrees to inclusion for data collection, the Subject Informed Consent will be signed and recorded in the Subject's records at Visit 1.

The Subject will be assigned a unique study identifier.

Data to be collected during the visit:

- Screening data as required by the inclusion/exclusion criteria documented in Subject study records
- Medical History (including Physical Exam)
- Low Back pain descriptive characteristics
- 7 day recall of Average Low Back Pain VAS as reported by the Subject
- Work status evaluation
- Medications (all medications including indication)
- ODI
- EQ-5D
- DASS₂₁
- Healthcare Utilization

Activities to be performed:

- Journal:
 - Instruct the Subject in the use of the Journal and provide the Journal.
- Prone Instability Test to assess lumbar multifidus dysfunction.
- Answer any questions the Subject may have, and confirm willingness to proceed if the baseline criteria are verified.
- Verify that the inclusion/exclusion criteria are satisfied.

- An MRI of the lumbar region of the low back will be performed or ordered if there are no MRI images from more recently than 180 days prior to Visit 1. MRI images will be reviewed^f to assess conditions that may be a possible cause of low back pain and to rule out possible surgical candidates by institutional guidelines.
- Pregnancy test in women of child bearing potential.
- Assessment by the Investigator of the Subject's suitability for ReActiv8 implant which includes review of the psychological assessment (e.g. mental fitness).

NOTE: The surgical assessment and other required assessments may be performed at any time prior to Visit 2, and still be included in the Visit 1 data collected. If the implanting physician determines that the Subject is not a suitable candidate for the procedure, then the Subject shall not be scheduled for implant, will be withdrawn from the Trial, and will not be included in the analysis.

- If the Subject meets the inclusion criteria, schedule the surgery for the ReActiv8 implant and discuss with the Subject. Ensure that all hardware necessary for the procedure is available, and schedule support staff.

6.2. Visit 2: Implant Procedure

The implant procedure should take place as soon as possible following the verification of baseline criteria, at a minimum of 1 day and maximum of 45 days following Visit 1. The duration of the implant procedure visit depends on local institutional practices and Subject condition post-implant, and may be as short as a few hours (e.g.: for an outpatient procedure), or as long as several days.

Data to be collected prior to implant:

- Medications

Data to be collected during or post implant:

- Surgical notes
- Adverse Events (including Adverse Events prior to the Implant Procedure, and any adverse events associated with the Implant Procedure).
- Measurement and recording of electrode impedance and stimulation thresholds as defined in the Implant and Programming Manual

NOTE: The Subject should preferably be unconscious (i.e.: general anesthesia) during assessment of electrode impedance and stimulation thresholds. If local anesthesia is used, then appropriate medication should be administered to minimize the chance that the Subject will remember the procedure.

Activities to be performed after implant procedure:

- Make a (de-identified) digital record of fluoroscopic images taken during the implant procedure^g including at least bi-plane (AP and lateral) radiographic images of electrode position that shows the entire implanted system from the distal tip of the electrodes to the whole IPG.

^f All Images to be de-identified and included in the data record for the Subject in an electronic format to allow analysis at a later date. A core lab may be used for evaluation of MRI images as part of the supplementary data analysis.

^g It is a requirement for a site to participate in the trial that digital recording of fluoroscopic images should be available

- Inspect the surgical site prior to hospital discharge
- Program IPG to OFF (i.e.: default state is no electrical output from the IPG).

NOTE: Regular post-surgical follow up per institutional guidelines in the first 7 days post-implant are included in the Implant Procedure Visit.

6.3. Visit 3: Post-Implant 7 -0+10 Days

A Post-Surgical Follow Up visit should be performed between 7 and 17 days post-implant.

Data to be collected

- Adverse Events

Activities to be performed:

- Examination of the surgical wounds (Physical Exam and Surgical Site Exam)
- General post-surgical clinical care
- Removal of sutures (Note: it is recommended that sutures be removed no sooner than 11 days post-implant to reduce the risk of infection)

6.4. Visit 4: Randomization & Activation Visit 14 ± 3 days Post Implant

Randomization shall be 14 ± 3 days from the date of implant (to allow for scheduling). Visit 3 and Visit 4 may be combined.

If the Subject is unable to use the device for any reason (e.g.: injury, infection, other new clinical condition) at the time of the Randomization Visit, then the Randomization Visit may be postponed up to 30 days to allow the issue to resolve without incurring a protocol deviation.

Note: A decision to delay randomization must be done before the Subject is randomized.

Data to be collected:

- Adverse events

Activities to be performed:

- Inspect surgical wound to verify healing, and remove sutures (if not previously removed). Address any clinical issues associated with the surgical procedure (Physical Exam and Surgical Site Exam)
- Confirm Subject allocation to Treatment or Control group has been completed.

For Subjects in the Treatment Group Only:

- Perform electrode impedance and threshold measurements and record results
- Program IPG to Subject appropriate levels

For Subjects in the Control Group Only:

- Program IPG to Control

For all Subjects:

- Train in use of the Activator and document assessment of Subject's ability to self-administer therapy twice a day starting the next day.
- Train in the procedure to deliver stimulation, including time of day and Subject positioning.

- Provide encouragement to contact site personnel if any difficulty is encountered delivering stimulation or completing a Session.

6.5. Visit 5: 14±7 Days Post Randomization

Data to be collected:

- Single point average low back pain VAS over previous week as reported by the Subject
- Adverse events
- AP and lateral X-Rays that clearly shows the entire implanted system from the distal tip of the electrodes to the whole IPG.

Activities to be performed:

- Inspection of surgical site (Physical Exam and Surgical Site Exam)
- Provide the pain Journal and instruct the Subject in the use of the Journal for 7 days prior to the next scheduled visit.
- Remind Subject to continue to lie down and activate therapy twice daily.
- Readout from IPG of stimulation delivery times and duration (compliance assessment), battery state, and stored impedance measurements

Note: Provide encouragement to all Subjects to continue to apply therapy using the Activator twice a day. If compliance assessment shows <90% compliance, additional counseling may be provided.

For Subjects in the Treatment Group Only:

- Device activities:
 - Electrode impedance and threshold measurements, and data collection
 - Adjustment of stimulation configuration and amplitude as appropriate

6.6. Visit 6: 45±7 Days Post Randomization

Data to be collected:

- Pain Journal:
 - VAS for daily average low back pain
- 7 day recall of Average Low Back Pain VAS as reported by the Subject
- Pain medications prescribed and taken
- Low Back Pain descriptive characteristics
- Work status evaluation
- Adverse events

Activities to be performed:

- Inspection of surgical site (Physical Exam and Surgical Site Exam)
- Collect Journal, and provide new Journal and instruct the Subject to continue to complete Journal assessments 7 days prior to the next scheduled visit.
- Remind Subject to continue to lie down and activate therapy twice daily.
- Readout from IPG of stimulation delivery times and duration (compliance assessment), battery state, and stored impedance measurements

Note: Provide encouragement to all Subjects to continue to apply therapy using the Activator twice a day. If compliance assessment shows <90% compliance, additional counseling may be provided.

For Subjects in the Treatment Group Only:

- Device activities:
 - Electrode impedance and threshold measurements, and data collection
 - Adjustment of stimulation configuration and amplitude as appropriate

6.7. Visit 7: 75±10 Days Post Randomization

Data to be collected:

- Pain Journal:
 - VAS for daily average low back pain
- 7 day recall of Average Low Back Pain VAS as reported by the Subject
- Low Back Pain descriptive characteristics
- Work status evaluation
- Oswestry Disability Index
- EQ-5D
- Pain medications prescribed and taken
- Percent Pain Relief
- Adverse events
- Subject Global Impression of Change (SGIC)
- Treatment Satisfaction Questionnaire (TSQ)
- Clinical Global Impression – Global Improvement (CGI-I)

Activities to be performed:

- Inspection of surgical site (Physical Exam and Surgical Site)
- Collect Journal, and provide new Journal and instruct the Subject to continue to complete Journal assessments 7 days prior to the next scheduled visit.
- Remind Subject to continue to lie down and activate therapy twice daily.
- Readout from IPG of stimulation delivery times and duration (compliance assessment), battery state, and stored impedance measurements

Note: Provide encouragement to all Subjects to continue to apply therapy using the Activator twice a day. If compliance assessment shows <90% compliance, additional counseling may be warranted.

For Subjects in the Treatment Group Only:

- Device activities:
 - Electrode impedance and threshold measurements, and data collection
 - Adjustment of stimulation configuration and amplitude as appropriate

6.8. Visit 8: 120 -0/+20 Days Post Randomization

This Primary Endpoint Assessment Visit must be performed no sooner than 120 days post randomization to ensure all Subjects have at least 120 days of treatment or control. At this visit Subjects in the Control group may now be programmed to appropriate stimulation levels and will be considered part of the Crossover group.

Data to be collected:

- Pain Journal
 - VAS for daily average low back pain
- 7 day recall of Average Low Back Pain VAS as reported by the Subject
- Low Back Pain descriptive characteristics
- Work status evaluation
- Oswestry Disability Index
- EQ-5D
- Pain medications prescribed and taken
- Percent Pain Relief
- Subject Global Impression of Change (SGIC)
- Treatment Satisfaction Questionnaire (TSQ)
- Clinical Global Impression – Global Improvement (CGI-I)
- Adverse events
- Blinding Assessment

Activities to be performed after endpoint data collection:

- Collect Subject's Journal
- Inspection of surgical site (Physical Exam and Surgical Site Exam)
- Device activities:
 - Electrode impedance and threshold measurements
 - Readout from IPG of stimulation delivery times and duration (compliance assessment), battery state, and stored impedance measurements
 - Adjustment of stimulation configuration and amplitude as appropriate
- For Subjects in the Control group, assessment of thresholds and programming of the ReActiv8 IPG to a Subject appropriate level that result in strong smooth contractions of the multifidus. These Subjects now form the Crossover Group.

Note: At the Primary Endpoint Assessment Visit, all Subjects are advised that they can vary their medications for back pain as needed or desired.

6.9. Visit 8a: Crossover and Activation

Subjects in the Crossover Group require additional activities and data collection, which may be done as part of Visit 8 or can be scheduled as an additional visit.

Data to be collected:

- Adverse events (after threshold assessment and IPG programming)

Activities to be performed:

- Device activities (if not already done):
 - Readout from IPG of stimulation delivery times and duration (compliance assessment), battery state, and stored impedance measurements

- Electrode impedance and threshold measurements, and data collection

Adjustment of stimulation configuration and amplitude as appropriate

6.10. Visit 9: 180 ± 30 Days Post Randomization

Data to be collected:

- 7 day recall of Average Low Back Pain VAS as reported by the Subject
- Low Back Pain descriptive characteristics
- Work status evaluation
- Oswestry Disability Index
- EQ-5D
- Pain medications prescribed and taken
- Percent Pain Relief
- Adverse event
- Device measurements and stimulation thresholds
- Subject Global Impression of Change (SGIC)
- Treatment Satisfaction Questionnaire (TSQ)
- Clinical Global Impression – Global Improvement (CGI-I)
- Health care Utilization

Activities to be performed:

- Inspection of surgical site (Physical Exam and Surgical Site Exam)
- Device activities:
 - Readout from IPG of stimulation delivery times and duration (compliance assessment), battery state, and stored impedance measurements
 - Electrode impedance and threshold measurements, and data collection
 - Adjustment of stimulation configuration and amplitude as appropriate

6.11. Visits 10: 240 ± 30 Days Post Randomization

Data to be collected:

- 7 day recall of Average Low Back Pain VAS over previous week as reported by the Subject
- Low Back Pain descriptive characteristics
- Work status evaluation
- Oswestry Disability Index
- EQ-5D
- Pain medications prescribed and taken
- Percent Pain Relief
- Adverse event
- Device measurements and stimulation thresholds
- Subject Global Impression of Change (SGIC)
- Treatment Satisfaction Questionnaire (TSQ)
- Clinical Global Impression – Global Improvement (CGI-I)
- Health care Utilization

Activities to be performed:

- Inspection of surgical site (Physical Exam and Surgical Site)

- Device activities:
 - Readout from IPG of stimulation delivery times and duration (compliance assessment), battery state, and stored impedance measurements
 - Electrode impedance and threshold measurements, and data collection
 - Adjustment of stimulation configuration and amplitude as appropriate

6.12. Visits 11: 12 Months 0-30/+60 Days Post Randomization

Data to be collected:

- 7 day recall of Average Low Back Pain VAS as reported by the Subject
- Low Back Pain descriptive characteristics
- Work status evaluation
- Oswestry Disability Index
- EQ-5D
- Pain medications prescribed and taken
- Percent Pain Relief
- Adverse events
- Device measurements and stimulation thresholds
- Subject Global Impression of Change (SGIC)
- Treatment Satisfaction Questionnaire (TSQ)
- Clinical Global Impression – Global Improvement (CGI-I)
- Health care Utilization

Activities to be performed:

- Inspection of surgical site (Physical Exam and Surgical Site Exam)
- Device activities:
 - Readout from IPG of stimulation delivery times and duration (compliance assessment), battery state, and stored impedance measurements
 - Electrode impedance and threshold measurements, and data collection
 - Adjustment of stimulation configuration and amplitude as appropriate

6.13. Annual Follow Up

All Subjects will be scheduled for an Annual Follow Up following Visit 11 until such time as ReActiv8 obtains US regulatory approval or the Trial is abandoned. Following US regulatory approval, all Subjects who continue with ReActiv8 implanted will have continuing Annual Follow Up for 7 years from the date of randomization.

Data to be collected:

- 7 day recall of Average Low Back Pain VAS as reported by the Subject
- Low Back Pain descriptive characteristics
- Work Status Evaluation
- Oswestry Disability Index
- EQ-5D
- Pain medications prescribed and taken
- Percent Pain Relief
- Adverse events
- Subject Global Impression of Change (SGIC)

- Treatment Satisfaction Questionnaire (TSQ)
- Clinical Global Impression – Global Improvement (CGI-I)
- Health care Utilization Inspection of surgical site (Physical Exam and Surgical Site)
- Device measurements and stimulation thresholds
- Device activities:
 - Readout from IPG of stimulation delivery times and duration (compliance assessment), battery state, and stored impedance measurements
 - Electrode impedance and threshold measurements, and data collection
 - Adjustment of stimulation configuration and amplitude as appropriate

6.14. Unscheduled Visits

If an unscheduled visit occurs for any reason, the following data will be collected prior to any other activities.

- 7 day recall of Average Low Back Pain VAS as reported by the Subject
- Adverse events

Activities to be performed:

- Inspection of surgical site (Physical Exam and Surgical Site Exam)

If an unscheduled visit occurs because of a suspected Adverse Device Effect (ADE) related to stimulation, then device testing shall be performed to investigate a suspected device failure.

Other activities to investigate the suspected ADE (e.g.: X-Ray imaging) may be performed at the discretion of the physician.

If an unscheduled visit occurs to perform a device explant for any reason (e.g.: infection necessitating device removal, elective removal at the request of the Subject), then additional data including surgical notes may be collected. Furthermore, any explanted devices or components shall be returned to the Sponsor following appropriate decontamination procedures.

Note: If an unscheduled visit occurs prior to the Endpoint Data Assessment Visit for a Subject in the Control group, then all efforts shall be made to avoid potential unblinding of the Subject, particularly as a result of IPG testing which may inadvertently result in delivery of stimulation leading to Subject-perceived muscle contraction.

6.15. Telephone Calls or Electronic contact

The study coordinator will contact Subjects by telephone (or electronically) prior to each study visit starting with the 75 day visit through the 12 month visit. This contact will be to check on the well-being of the Subject, remind the Subject of the upcoming visit, remind Subjects to contact the Investigator/staff should he/she have any questions or concerns, remind Subjects to keep their pain medications the same as those taken at baseline, and to complete the pain Journal 7 days prior to the 120 day visit. The telephone calls (or electronic contact) should be made within 15-25 days prior to the scheduled visit date.

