Crossover and Open Label Phase	
Following endpoint assessment at the Primary Endpoint Assessment Visit:
 
 • Subjects randomized to the Control Arm will have ReActiv8 configured to deliver stimulation at a Subject-appropriate level, and Subjects will be instructed to deliver stimulation in two 30-minute sessions per day. Once the Control group has crossed over, it will be referred to as the Crossover group. • All Subjects in the Treatment group will be advised to continue to use their devices for two 30-minute sessions per day. • All Subjects will be permitted to change their medications
Primary Efficacy Endpoint	The Primary Efficacy Endpoint is a comparison of responder rates between Treatment and Control groups, where a “responder” is a Subject with $\geq 30\%$ reduction from baseline in average low back pain VAS without any increase in pain medication and/or muscle relaxants prescribed and taken in the two weeks prior to the Primary Endpoint Assessment Visit.
Secondary Efficacy Endpoints	
The hypotheses will be tested utilizing an overall Type I error of 5%. The overall Type I error will be maintained by utilizing Hochberg’s method to test the collection of the first five secondary objectives. These will be tested only if the primary efficacy endpoint is met.
 
 1. Comparison of change from baseline in ODI between Treatment and Control groups at the Primary Endpoint Assessment Visit 2. Comparison of change from baseline in EQ-5D between Treatment and Control groups at the Primary Endpoint Assessment Visit 3. Comparison of Percent Pain Relief between Treatment and Control groups reported by the Subject at the Primary Endpoint Assessment Visit 4. Comparison of Subject Global Impression of Change at the Primary Endpoint Assessment Visit 5. Comparison of number of Subjects with Resolution of Low Back Pain (remitters or cure, defined as a VAS score ≤ 2.5cm) at the Primary Endpoint Assessment Visit 6. Evaluation of changes in primary and secondary efficacy metrics in Crossover Group following the Outcome Post Crossover Visit.

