Study Schedule	
 • Informed consent, baseline criteria verification, • ReActiv8 implant (1-45 days post inclusion) • Post-Implant Follow-up: 7 days -0/+10 days post-implant. • Randomization and Activation Visit: 14±3 days post-implant • 14 day visit: 14 ± 7 days post-randomization • 1.5 month visit: 45 ± 7 days post-randomization • 2.5 month visit: 75 ± 10 days post-randomization • 4 month visit: 120 -0/+20 days post-randomization - Primary Endpoint Assessment Visit • 6 month visit: 180 ± 30 days post-randomization • 8 month visit: 240 ± 30 days post-randomization • 12 month visit: 360 -30/+ 60 days post-randomization • Annual follow up every 360 ± 60 days post-randomization until Study Closure 
For Subjects in the Control group, after the Subject completes the endpoint assessment at the Primary Endpoint Assessment Visit, the ReActiv8 will be programmed to deliver stimulation at a Subject-appropriate level, and other activities will be performed.

	
The study will be considered complete with regard to the primary endpoint after the required numbers of randomized Subjects have completed the Primary Endpoint Assessment Visit.

Adjunctive Therapies
	
 • All medications for treatment of low back pain will be stabilized 30 days prior to the Baseline Visit and remain stabilized through the Primary Endpoint Assessment Visit. • All other treatments for low back pain (e.g. interventional pain treatments, chiropractic) will be prohibited until after the Primary Endpoint Assessment Visit.

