4.7.1. Primary Endpoint – Low Back Pain VAS

The Primary Efficacy Endpoint is a comparison of responder rates between Treatment and Control groups, where a “responder” is a Subject with $\geq 30\%$ reduction from baseline in average low back pain VAS without any increase from baseline in pain medication and/or muscle relaxants prescribed and taken in the two weeks prior to the Primary Endpoint Assessment Visit.

Note: The primary outcome measure is intended to assess the efficacy of 120 days of stimulation. Thus the visit for assessment of the primary outcome must occur no sooner than 120 days post randomization.

Records of pain medications will be collected along with all other medications used for treatment of low back pain, which are also being collected for analysis of secondary and cost-effectiveness endpoints. The Subject will report medications taken at each scheduled follow-up visit. Rescue medications taken on an exceptional basis for acute pain conditions other than back pain will also be documented and their possible effect examined as part of sensitivity analyses.

After the Primary Endpoint Assessment Visit, Subjects will be permitted to adjust their drug use as appropriate, based on consultation with their physicians, and data on drugs prescribed and taken will continue to be collected.

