5.3. Other Therapy During the Trial

5.3.1. Medication

Subjects shall be advised to not make any change to medications for treatment of low back pain at the time of the Subject's inclusion in the Trial until the Primary Endpoint Assessment Visit. This includes medications for pain and muscle relaxants. Subjects will be informed that they may reduce, increase or discontinue medications for low back pain following the Primary Endpoint Assessment Visit.

Subjects will be informed that if they believe they need any change in prescription medications for treatment of low back pain during the Trial, then they should contact the Investigator who will arrange for modification of type or dose of pain medications, as clinically necessary, and the data will be recorded. Subjects will be told that they should not request modification to prescribed drugs for their low back pain from any non-study physician during the period from baseline until the Primary Endpoint Assessment Visit. Any change in medications for other conditions (e.g.: hypertension) are allowed if prescribed by the Subject's regular treating physician.

All Subjects shall continue on any and all prescribed medication deemed medically necessary and not prescribed for the indication of CLBP (e.g.: antihypertensive medicines, statins, thyroid medications, diabetes medication, and low-dose aspirin).

Any change in pain medication prescribed and taken over the 14 days prior to the 120 day visit shall be reported by the Subject at the visit. If the prescribed dose is PRN, the Subject shall report the use of the drug over the prior two weeks if it changed from that taken at baseline.

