8.10. Health Economics

Cost-effectiveness of ReActiv8 therapy, extrapolated to the lifetime of the device, will be measured. Key economic outcome measures to be recorded will be:

- Change in work status at all visits.
- Change in consumption of medications taken for low back pain at all visits compared to Baseline. Note that an analysis may be performed of different categories of medications including for example opioids, muscle relaxants and anti-depressants.
- Assessment of health care utilization (office visits, hospital visits, emergency room visits, and other therapies such as physical therapy) at all visits.

Note that both the Treatment and Control group Subjects are required to keep medications constant from randomization until the Primary Endpoint Assessment Visit, and other health care utilization will be as per the protocol (e.g.: no additional therapies).

Following the Primary Endpoint Assessment Visit, all Subjects will be permitted to adjust medications and to use other health care resources. For the Crossover Group, this may yield some information on how Subjects will adjust medications during the treatment phase.

Note that completion of the Health Economics assessments is likely to be incomplete at the time of PMA submission for ReActiv8, since not all Subjects will have reached the 12 month point at that time.

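### Section 6.15 reminds Subjects to hold pain medication at the Baseline level up to 12 months, although they are free to change it after Visit 8: 3 of the 5 contacts contradict the medication rule

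*Protocol*

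**What the plan says.** Protocol 6.15 requires a telephone or electronic contact "prior to each study visit starting with the 75 day visit through the 12 month visit", made 15 to 25 days before the scheduled visit. It gives a single list of purposes for these contacts: check well-being, announce the visit, invite questions, "remind Subjects to keep their pain medications the same as those taken at baseline", and prompt completion of the pain Journal before the 120-day visit. The Journal item is tied to a visit. The medication item is not.

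The medication rule itself is stated in several other places, always with the same end point:

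- Protocol Table 1, Adjunctive Therapies: medications for low back pain "remain stabilized through the Primary Endpoint Assessment Visit".
- Protocol Table 1, Crossover and Open Label Phase, after the endpoint assessment: "All Subjects will be permitted to change their medications".
- Protocol 4.7.1: "After the Primary Endpoint Assessment Visit, Subjects will be permitted to adjust their drug use as appropriate".
- Protocol 5.3.1: "Subjects will be informed that they may reduce, increase or discontinue medications for low back pain following the Primary Endpoint Assessment Visit".
- Protocol 6.8, at Visit 8: "all Subjects are advised that they can vary their medications for back pain as needed or desired".
- SAP 8.10, with matching text in Protocol 4.7.6: "Following the Primary Endpoint Assessment Visit, all Subjects will be permitted to adjust medications and to use other health care resources".

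**The concern.** A Subject is told in person at Visit 8 that back-pain medication may now be varied. Read as written, 6.15 then has the coordinator say the reverse before each of the next three visits.

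Medication use after Visit 8 is planned data. Change in opioids from Baseline to 12 months is a supporting analysis (Protocol 4.7.5, SAP 8.9). Medication consumption at all visits is a key health-economic outcome (Protocol 4.7.6, SAP 8.10), and 4.7.6 notes that the release after Visit 8 may be informative about how the Crossover Group adjusts. A repeated request not to change medication works against the behaviour these analyses are meant to observe. It also leaves Subjects, some of them on opioids, with conflicting direction.

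**Working it through.** The plan states no number of contacts, so there is no figure to reproduce. The check is a count and a calendar.

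**Inputs.** Visit days come from the Study Schedule row of Protocol Table 1: Visit 7 at day 75 ± 10, Visit 8 at day 120 −0/+20, Visit 9 at day 180 ± 30, Visit 10 at day 240 ± 30, Visit 11 at day 360 −30/+60. Contact timing, 15 to 25 days before the scheduled visit, comes from 6.15.

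**Formulas.** Contact day = scheduled visit day − 25 to scheduled visit day − 15. Days after Visit 8: minimum = earliest contact − 140, maximum = latest contact − 120.

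With visits at their target days, and Visit 8 anywhere in its window:

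| Contact before | Contact day | Days after Visit 8 | Reminder consistent with the rule? |
|---|---|---|---|
| Visit 7 | 75 − 25 to 75 − 15 = 50–60 | before Visit 8 | yes |
| Visit 8 | 120 − 25 to 120 − 15 = 95–105 | before Visit 8 | yes |
| Visit 9 | 180 − 25 to 180 − 15 = 155–165 | 155 − 140 = 15 to 165 − 120 = 45 | no |
| Visit 10 | 240 − 25 to 240 − 15 = 215–225 | 215 − 140 = 75 to 225 − 120 = 105 | no |
| Visit 11 | 360 − 25 to 360 − 15 = 335–345 | 335 − 140 = 195 to 345 − 120 = 225 | no |

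Two of five contacts carry a correct reminder and three a contradictory one.

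**Sensitivity to visit windows.** The contact is counted back from the scheduled date, which may lie anywhere in the window. Letting Visits 9 to 11 range over their full windows gives:

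- Visit 9 (day 150–210): contact day 125–195, which is 125 − 140 = −15 to 195 − 120 = 75 days after Visit 8.
- Visit 10 (day 210–270): contact day 185–255, which is 185 − 140 = 45 to 255 − 120 = 135 days after.
- Visit 11 (day 330–420): contact day 305–405, which is 305 − 140 = 165 to 405 − 120 = 285 days after.

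Only the Visit 9 contact can precede Visit 8, and only when Visit 9 is scheduled near the early edge of its window and Visit 8 is held late. The contacts before Visits 10 and 11 always follow an in-window Visit 8.

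**Sensitivity to Visit 8a.** Protocol 6.9 lets the crossover activation be a separate visit. If that visit also gets a contact, a Crossover Subject could have six contacts, up to four of them contradictory.

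**The case against.** The strongest reply is that the protocol, read as a whole, leaves no doubt about the rule: medication is stable to Visit 8 and free afterwards, and Subjects are told so. On this view 6.15 merely fails to repeat a limit set elsewhere. Its list also cannot be a script for every call, because the Journal item makes no sense after the 120-day visit. A coordinator who drops that item after Visit 8 has equal reason to drop the medication item beside it. No call script is in the documents, so what Subjects would actually hear is unknown.

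Part of this stands. The intended rule is clear, and the error is one of drafting. But the other sections limit the medication rule, not the reminder. The reference to the 120-day visit belongs to the Journal clause; a medication rule that runs from inclusion would not be expressed as seven days before a visit. The one item with a limit makes the lack of a limit on its neighbour more noticeable. Nor should the plan depend on coordinators departing from it, since Protocol 9.2 requires prior Sponsor approval for non-emergency deviations.

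The second reply is that little is at stake. The outcomes affected are untested and may be incomplete at PMA submission, the sham comparison ends at Visit 8, both arms get the same contacts, and 4.7.1 leaves drug changes to consultation with physicians. This limits the importance of the point, and 4.7.6 also records that some ReActiv8-A subjects reduced medication despite being told to keep it constant. But giving the reminder to both arms does not remove its influence from a change from Baseline within a group, which is what remains after crossover.

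**Conclusion.** The concern holds. As written, 3 of the 5 contacts in 6.15 contradict the medication rule given in Protocol Table 1, 4.7.1, 4.7.6, 5.3.1 and 6.8 and in SAP 8.10. The count assumes visits at their target days and no separate Visit 8a. An early Visit 9 with a late Visit 8 could bring it to two of five, and a separate Visit 8a could bring it to four of six.

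The effect on 12-month opioid change or on medication consumption cannot be quantified from the documents, and its net direction is unknown because the reminder could hold back decreases and increases alike. The day-120 primary endpoint and the five tested secondary endpoints are not affected, and for them the reminders before Visits 7 and 8 are right. This is an operative instruction that should be corrected; it is not a threat to the confirmatory result.

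**What to change.** In Protocol 6.15, limit the constant-medication reminder to the contacts before Visits 7 and 8. State that the contacts before Visits 9, 10 and 11, and before Visit 8a if it is held separately, carry no such reminder and are consistent with 5.3.1 and 6.8. The Journal item is already tied to the 120-day visit, so restating its limit in the same sentence would only be tidying.

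The cost is one sentence, plus the call script if one is in use. The reminder stays in place up to the primary endpoint. If contacts after Visit 8 have already been made as written, say so as a limitation of the 12-month opioid analysis and the health-economic medication analyses.
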